3.7.2.4 Electrocardiogram Assessments

At the prespecified time points, a rest 12-lead ECG will be recorded using the ECG monitor provided by the central ECG measurement facility and according to the procedure specified by the facility. However, if the serum potassium is confirmed to exceed 5.5 mEq/L at the trial site or the central laboratory at any time point in the period with no specified 12-lead ECG, a 12-lead ECG will be performed as an unscheduled examination. The investigator or subinvestigator will interpret each ECG chart as normal or abnormal, and record the status (measured/ not measured), the date of recording, as well as the interpretation (normal or abnormal [details, if abnormal]) in the source document and the eCRF.

The ECG record will be sent to the central ECG measurement facility to measure the heart rate, RR interval, PR interval, QRS axis, QT interval, and QTc (QT corrected for heart rate) interval (QTcB, QTcF). The central ECG measurement facility will in turn send the 12-lead ECG analysis report to the investigator or subinvestigator.

The investigator or subinvestigator will reconfirm the interpretation of the 12-lead ECG referring to the analysis report, which will then be signed and retained.

The electronic file of the 12-lead ECG analysis report provided to the sponsor by the central ECG measurement facility will be used as the source document; therefore, entry of the heart rate, RR interval, PR interval, QRS axis, QT interval, and QTc interval (QTcB, QTcF) in the eCRF will be unnecessary.

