3.8.3.2 Documenting Reasons for Treatment Discontinuation

A subject may discontinue participation in the trial at any time, and the investigator or subinvestigator may discontinue a subject's participation in the trial if medically necessary. Subjects who fall under any of the following must be withdrawn from the trial. If a subject discontinues treatment, a single reason for the discontinuation (the main reason) will be recorded in the eCRF.

1) Reasons related to AE:

- Subject decides to discontinue because of annoyance or discomfort due to a non-serious AE which is not otherwise determined to be an undue hazard
- AST or ALT value is ≥ 3 times the upper limit of normal (ULN).
- Serum or plasma sodium concentration measured at the trial site or the central laboratory increases by ≥ 12 mEq/L from immediately predose within 24 hours after start of the IMP administration.
- The serum or plasma sodium concentration measured at the trial site or the central laboratory is ≥ 155 mEq/L during the treatment period.
- The onset of drug-induced hypersensitivity is suspected.

- Any severe AESI (feeling abnormal, feeling hot, erythema, hyperhidrosis, pruritus, rash, urticaria, nausea, epigastric discomfort, or dyspnea) occurs.
- Continuing IMP places the subject at undue risk as determined by the investigator or subinvestigator (eg, a safety concern that is possibly, probably, or likely related to IMP).
 - Serious adverse event
 - Other potentially IMP-related safety concerns or AEs

- 2) Withdrawal of informed consent by the subject (when it is confirmed to be unrelated to AEs)
- 3) Protocol deviations (other than poor compliance with the IMP administration rules)
 - Deviations related to the inclusion or exclusion criteria
 - Deviations related to prohibited concomitant medications
- 4) Judgment by the investigator or subinvestigator (for the reasons other than an AE)
- 5) Death
- 6) Lost to follow-up
- 7) Pregnancy (see [Section 5.5](#))
- 8) Technical problems (eg, malfunctions of medical devices)
- 9) Premature termination of the entire or part of the trial by the sponsor

If the subject discontinues IMP due to an AE, the investigator, subinvestigator, or other trial personnel, will make every effort to follow the event until it has resolved or stabilized, or until the subject is lost to follow-up or has died.

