### **3.4 Handling of Time Points**

Case report form (CRF) Visit values at each time point (time points from baseline in the screening, treatment, and follow-up periods as specified in the protocol Table 3.7.1) will be used in summaries (but values at the time of discontinuation will not be used in summaries). Unscheduled Visit values will not be used.

According to the rules specified in the protocol [Section 3.2.3](#), for the completion assessment of subjects who have completed treatment after a treatment period of shorter than 5 days, the CRF Visit will be set to correspond with the day of assessment for the analysis visit. Concerning interval urine samples, the daily urine volume will be calculated by summing all the interval urine volumes that constitute the daily urine volume for that day. If the interval urine sample is the last one for that day, the corresponding interval will be set as the analysis interval. The same rules also apply to fluid intake and urine electrolyte excretion. Other variables specified in the corresponding CRF Visit to be measured multiple times will be set to precede IMP administration.

Baseline and final administration time point for each variable are defined as follows.

Table 3.4-1 Handling of Time Points		
Variable	Baseline	Final Administration Time Point
Clinical laboratory value	Before IMP administration on Day 1	Day after final IMP administration
Vital signs	Before IMP administration on Day 1 (Screening values will be used if the values at screening are measured on Day 1 but not measured prior to the IMP administration on that day.)	Day after final IMP administration
12-lead ECG	Before IMP administration on Day 1	Day after final IMP administration
Daily urine volume, daily fluid intake, daily fluid balance	Within 24 hours before IMP administration on Day 1	-
Serum sodium concentration, serum potassium concentration, serum osmolality	Before IMP administration on Day 1	-
Daily urine sodium excretion, daily urine potassium excretion	Within 24 hours before IMP administration on Day 1	-
Urine osmolality	Within 24 hours before IMP administration on Day 1	-
Biomarkers (plasma AVP concentration, plasma renin activity, plasma brain natriuretic peptide [BNP] concentration, serum N-terminal pro-brain natriuretic peptide [NT-proBNP] concentration, and serum troponin I concentration)	Before IMP administration on Day 1	Day after final IMP administration

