### **9.3 Clinical Laboratory Data**

Clinical laboratory data obtained from central measurements will be used for analyses. For clinical laboratory test parameters other than qualitative urinalysis, measured values and changes from baseline at each time point and at the time of final IMP administration will be summarized using descriptive statistics. For qualitative urinalysis parameters, shift tables will be prepared at each time point and at the time of final IMP administration compared with baseline. In addition, measured values of clinical laboratory test parameters other than qualitative urinalysis will be categorized as below, within, or above the normal range, and shift tables will be prepared at each postdose time point and at the time of final IMP administration compared with baseline.

The numbers and percentages of subjects who have a visit with serum total bilirubin value of  $\geq 2$  times the upper limit of normal (ULN), and an aspartate aminotransferase (AST) or alanine aminotransferase (ALT) value of  $\geq 3$  times the ULN at any postdose time point will be calculated.

The numbers and percentages of subjects experiencing the following events after IMP administration will be calculated.

- A serum sodium concentration  $>147$  mEq/L
- A  $>10$  mEq/L increase in serum sodium concentration within 24 hours after the start of IMP administration

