### **9.6 Electrocardiogram Data**

For 12-lead ECG parameters, measured values and changes from baseline will be summarized at each time point and at the time of final IMP administration using descriptive statistics.

The numbers and percentages of subjects who have a QT corrected for heart rate (QTc) interval of >450, >480, or >500 msec at any postdose time point until the time of final IMP administration will be calculated. The numbers and percentages of subjects who have a change in QTc interval from baseline of >30 and >60 msec at any postdose time point or at the time of final IMP administration will be calculated. Also at baseline and at each postdose time point, the numbers and percentages of subjects will be calculated in the same manner as described above.

A shift table showing interpretation (normal or abnormal) will be prepared at each postdose time point and at the time of final IMP administration compared to baseline. Interpretation (normal or abnormal) assessments by the trial site (investigator or subinvestigator) will be used.

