- CT-10.1.3 Mean Change from Baseline in Clinical Laboratory Test Results (Urinalysis) (Safety Analysis Set)
- CT-10.2 Shift Tables of Clinical Laboratory Test Results (Qualitative Urinalysis) (Safety Analysis Set)
- CT-10.3.1 Shift Tables of Clinical Laboratory Test Results (Serum Chemistry) (Safety Analysis Set)
- CT-10.3.2 Shift Tables of Clinical Laboratory Test Results (NA, K) (Safety Analysis Set)
- CT-10.3.3 Shift Tables of Clinical Laboratory Test Results (Hematology) (Safety Analysis Set)
- CT-10.3.4 Shift Tables of Clinical Laboratory Test Results (Urinalysis) (Safety Analysis Set)
- CT-10.4.1 Listing of Abnormal Laboratory Findings (IMP Administered Subjects)
- CT-10.4.2 Listing of Abnormal Laboratory Findings Potential Drug-Induced Liver Injury (IMP Administered Subjects)
- CT-10.5 Incidence of Potential Drug-Induced Liver Injury (Safety Analysis Set)
- CT-10.6 Incidence of Sodium Related Events (Safety Analysis Set)
- CT-11 Mean Change from Baseline in Vital Signs (Safety Analysis Set)
- CT-12.1 Mean Change from Baseline in Electrocardiogram Results (Safety Analysis Set)
- CT-12.2.1 Shift Table of 12-Lead ECG Findings (Normal/Abnormal Assessments) (Safety Analysis Set)
- CT-12.3.1 Incidence of Categorical Changes in Electrocardiogram Results (Post baseline any visit) (Safety Analysis Set)
- CT-12.3.2 Incidence of Categorical Changes in Electrocardiogram Results (Each Visit) (Safety Analysis Set)
- PDT-1.1 Descriptive Statistics for Daily Urine Volume (mL) (Pharmacodynamic Analysis Set)
- PDT-1.2.1 Descriptive Statistics for Interval Urine Volume (mL) (Pharmacodynamic Analysis Set)

PDT-1.2.2 Descriptive Statistics for Interval Urine Volume (mL) by Dose Escalation (Pharmacodynamic Analysis Set)

PDT-1.3.1 Descriptive Statistics for Cumulative Urine Volume (mL) (Pharmacodynamic Analysis Set)

PDT-1.3.2 Descriptive Statistics for Cumulative Urine Volume (mL) by Dose Escalation (Pharmacodynamic Analysis Set)

PDT-2.1 Descriptive Statistics for Daily Fluid Intake (mL) (Pharmacodynamic Analysis Set)

PDT-2.2.1 Descriptive Statistics for Interval Fluid Intake (mL) (Pharmacodynamic Analysis Set)

PDT-2.2.2 Descriptive Statistics for Interval Fluid Intake (mL) by Dose Escalation (Pharmacodynamic Analysis Set)

PDT-2.3.1 Descriptive Statistics for Cumulative Fluid Intake (mL) (Pharmacodynamic Analysis Set)

PDT-2.3.2 Descriptive Statistics for Cumulative Fluid Intake (mL) by Dose Escalation (Pharmacodynamic Analysis Set)

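### SAP 3.4 bars unscheduled values without exempting the any-postdose safety counts, so a QTc prolongation seen only on the potassium-triggered ECG goes uncounted

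*SAP*

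**What the plan says.** SAP 3.4 builds summaries from the scheduled case report form visits. It adds that "values at the time of discontinuation will not be used in summaries). Unscheduled Visit values will not be used", and states no exception.

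The threshold counts are worded more broadly. SAP 9.6 counts subjects whose QTc exceeds 450, 480 or 500 msec "at any postdose time point until the time of final IMP administration will be calculated", and counts QTc changes above 30 and 60 msec in similar terms. SAP 9.3 counts subjects with bilirubin at least 2 times and AST or ALT at least 3 "times the ULN at any postdose time point will be calculated". It also counts two sodium events after dosing: a value above 147 mEq/L, and a rise of more than 10 mEq/L within 24 hours. The corresponding outputs in SAP Appendix 1 are CT-10.5 (liver), CT-10.6 (sodium) and, for QTc, "CT-12.3.1 Incidence of Categorical Changes in Electrocardiogram Results (Post baseline any visit) (Safety Analysis Set").

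Protocol 3.7.2.4 requires an additional tracing when potassium exceeds 5.5 mEq/L in a period with no specified ECG: "a 12-lead ECG will be performed as an unscheduled examination". The same section says "The ECG record will be sent to the central ECG measurement facility to measure the heart rate" and the intervals, QTc included.

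**The concern.** A count of subjects who ever cross a safety threshold is normally taken over every valid postdose value. Here the SAP's general visit rule narrows that count to scheduled values, and it removes a measurement that the protocol itself orders because a safety signal has appeared. The omitted ECGs are not a random subset: each exists because potassium was high.

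The objective is tolerability and SAP 6.1 sets no primary outcome, so these tables carry part of the conclusion. If a prolongation appears in a listing but not in the any-visit incidence table, the report disagrees with itself, and the table is the one that reads low.

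**Working it through.** **1. The plan's own figures.** The documents give no figure for this point. The only stated probabilities are in SAP 4: 1 − 0.95^40 = 87.1% and 1 − 0.96^40 = 80.5%, which reproduce the stated 87% and 80%. They concern sample size and do not depend on the visit rule.

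**2. QTc: postdose schedule** (Protocol Table 3.7-1 and Sections 3.7.1.2 to 3.7.1.8).

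| Day | Potassium | ECG |
|---|---|---|
| 1 | 4 h, 8 h | 1 h |
| 2 | predose (also 4 h, 8 h if dose raised) | none |
| 3 | predose (also 4 h, 8 h if dose raised) | one |
| 4 | predose | none |
| 5 | predose | none |
| 6 or withdrawal | one | one |
| Follow-up | one | none |

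Days 2, 4 and 5 have potassium but no ECG. That is 1 + 1 + 1 = 3 samples, or 3 + 2 = 5 if the dose is raised on Day 2. A raise on Day 3 adds samples on a day that already has an ECG. I leave out the Day 1 samples at 4 h and 8 h, because it is unclear whether the trigger applies after that day's scheduled ECG. I also leave out follow-up, because the absolute QTc count stops at the final administration time point.

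The path is then direct. High potassium on Day 2, 4 or 5 leads to an ECG that the protocol calls unscheduled. The tracing goes to the central facility, since that instruction is not limited to scheduled ECGs. SAP 3.4 then bars the value, and a prolongation seen only there is absent from CT-12.3.1.

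**3. Liver.** Chemistry is scheduled postdose only at Day 6 or withdrawal and at follow-up. CT-10.5 needs both the bilirubin and the AST or ALT condition. Protocol 5.1 allows repeat or additional tests but does not say that they go to the central laboratory, and Protocol 3.7.2.2 describes central shipment for samples at prespecified times. Site results are excluded anyway, because SAP 9.3 uses central data only. The visit rule therefore bites only on unscheduled samples that were measured centrally, and the documents do not say how many there would be.

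**4. Sodium.** The same logic applies to CT-10.6. Central sodium is sampled every treatment day, so an unscheduled value matters only if no scheduled value also qualifies.

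**5. Withdrawal values.** SAP 3.4 bars values at discontinuation. Against that, Protocol 3.7.1.7 puts the withdrawal assessment on the day after the last dose, SAP Table 3.4-1 defines that same day as the final administration time point for laboratory values and ECG, and SAP 5.4 carries data forward to it. SAP 9.6 names the final administration time point in its QTc counts; the liver sentence in SAP 9.3 does not.

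**6. Size.** One missed subject is 1/40 = 2.5 points. As illustration, 1/40 has an exact 95% interval of 0.1% to 13.2%, and 0/40 has 0% to 8.8%. SAP 9 repeats the tables by presence or absence of dose escalation. Group sizes are not given; at assumed sizes of 30, 20 or 10, one subject is 3.3, 5.0 or 10.0 points.

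**The case against.** The best defence is that both exclusions were meant only to keep odd values out of visit columns. For withdrawal values this is persuasive. SAP 3.4 goes on to place early completers' assessments at analysis visits, and the passages in step 5 give the withdrawal value a home as the final administration value. A reader might infer that withdrawn subjects lose their last ECG and liver panel, all the more because AST or ALT at least 3 times the upper limit is on the list headed "Subjects who fall under any of the following must be withdrawn from the trial". The documents do not establish that loss. What remains is a gap in wording, chiefly for liver. For unscheduled values the defence is weaker, because the sentence is unqualified.

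A reader might also infer that every liver elevation on Days 2 to 5 escapes CT-10.5. That goes too far: subjects who finish or withdraw early have a scheduled panel on those days, and an isolated AST or ALT rise does not meet the composite under any visit rule.

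Third, the cases are not lost. Protocol 5.4 makes composite liver cases reportable as adverse events, and Protocol 5.1 does the same for laboratory values that lead to discontinuation. The listings include CT-10.4.1, "CT-10.4.2 Listing of Abnormal Laboratory Findings Potential Drug-Induced Liver Injury (IMP Administered Subjects") and PDATA-6.1 for central ECG results. This stands and limits the harm, but the protocol states no comparable reporting rule for QTc.

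Finally, excluding event-triggered measurements keeps ascertainment even. That is a legitimate choice, but the SAP does not give it as a reason, and it sits badly with a table titled as covering any visit.

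**Conclusion.** The concern holds for QTc on the text as written: a prolongation found only on the protocol-required, potassium-triggered ECG would not enter CT-12.3.1. For liver and sodium the same rule applies to unscheduled central values, but the documents do not show that such samples would be common. For withdrawal values there is an ambiguity, with the likely intent being to use them at the final administration time point.

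The direction is certain, because leaving values out can only lower the number of subjects counted. The size is not: 2.5 points per missed subject at N = 40, and possibly no subject missed. It is tempting to project the reach of the withdrawal question from phase 2 discontinuations for adverse events (2/48 on OPC-61815, 5/60 over all arms). The documents do not support that. Protocol 1.2.2 places the OPC-61815 cases in the 4-mg group and reports none at 8 mg or 16 mg, which is 0 of 12 + 11 = 23, and discontinuing is not the same as crossing a threshold.

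This is worth correcting before the tables are produced. It does not undermine the safety analysis as a whole.

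**What to change.** In SAP 3.4:

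- Limit the exclusions of unscheduled and discontinuation values to by-visit summaries.
- State that the counts in CT-12.3.1, CT-10.5 and CT-10.6 use all postdose values from the central laboratory or central ECG facility, including unscheduled and withdrawal-assessment values (for QTc, up to the final administration time point).
- Confirm that the withdrawal assessment supplies the final administration time point where Table 3.4-1 defines one.

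The cost is a few sentences and minor programming. Reported incidence may be slightly higher, and ascertainment becomes uneven because extra ECGs are triggered by events; a footnote to the tables should say so. If the sponsor prefers to keep the exclusion, the SAP should state and justify it for these counts and retitle CT-12.3.1 to show that it covers scheduled visits only.

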^eSerum sodium concentration (local measurement), serum potassium concentration (local measurement), body weight, chest x-ray, and vital signs (blood pressure, pulse rate, and body temperature): If measurements are performed on Day 1 as part of the screening examination, the measurements do not have to be repeated at predose on Day 1.

^fPerformed on the day that the dose is increased to 16 mg.

^gDyspnea: Respiratory rate, paroxysmal nocturnal dyspnea, orthopnea, and subject-assessed dyspnea (assessment of presence or absence of symptoms by subjects at screening)

^hCongestive symptom findings: Lower limb edema, hepatomegaly, jugular venous distension, pulmonary rales, and cardiac third sound

ⁱChest x-ray: Chest x-ray does not have to be repeated if it has been performed within 24 hours before informed consent. The results of chest x-ray performed prior to the acquisition of informed consent can be used to determine eligibility of the subject to participate in the trial.

^jLaboratory tests: At screening, laboratory tests are performed at the trial site.

^k If the serum potassium is confirmed to exceed 5.5 mEq/L at the trial site or the central laboratory at any time point in the period with no specified 12-lead ECG, a 12-lead ECG will be performed as an unscheduled examination.

^lPlasma concentrations of AVP and BNP, plasma renin activity, and serum concentrations of NT-proBNP and troponin I

^mDNA storage: In principle, blood sampling for DNA storage will be performed at predose on the day of initial IMP administration (Day 1). Informed consent for DNA storage must be obtained by the blood sampling for DNA storage. If blood sampling is not performed at that time or needs to be repeated, blood sampling will be performed at a feasible time during the trial period.

ⁿThe infusion solution will be checked and adjusted according to the specifications for each day (see [Section 3.7.1.2](#) to [Section 3.7.1.6](#)).

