3.7.1.2 Treatment Period (Day 1)

1) Predose

- Urine sodium concentration (central measurement)
- Urine osmolality (central measurement)
- Urine potassium concentration (central measurement)
- Serum sodium concentration (local measurement, central measurement)
- Serum potassium concentration (local measurement, central measurement)
- Serum osmolality (central measurement)
- Biomarkers (central measurement)
- Body weight
- Chest x-ray (cardiothoracic ratio and pulmonary congestion)
- Clinical laboratory tests (central measurement)
- Vital signs (blood pressure, pulse rate, and body temperature)

- 12-Lead ECG
- Blood sampling for DNA storage (central measurement)

If serum sodium concentration (local measurement), serum potassium concentration (local measurement), body weight, chest x-ray, and vital signs (blood pressure, pulse rate, and body temperature) are measured as the screening examination on Day 1, the measurements will not need to be repeated at predose on the same day.

2) Start of urine collection

Subject are required to urinate completely immediately before start of IMP administration to collect urinate at the time intervals shown in [Table 3.7.1.2-1](#). At the end of each interval, subject are required to urinate completely to start urine collection for the next interval.

Table 3.7.1.2-1 Urine Collection Intervals After Start of IMP administration on Day 1	
Urine collection interval	Allowable time window for the interval end
0 to 4 hours after start of IMP administration	+1 hour
4 to 8 hours after start of IMP administration	+4 hours
8 hours after start of IMP administration to immediately before IMP administration on the next day	

3) IMP administration

The investigator or subinvestigator will confirm that the subject meets all of the inclusion criteria and falls under none of the exclusion criteria, and administer the IMP to the subject.

4) Administration of diuretic agents

5) Examinations and tests after start of IMP administration

The examinations and tests shown in [Table 3.7.1.2-2](#) will be conducted at each time point.

Table 3.7.1.2-2 Examinations/Tests and Timing After Start of IMP Administration on Day 1		
Item	Timing	Allowable time window
Urine volume and fluid intake	0 to 1 hour after start of IMP administration	+15 minutes ^a
	1 to 2 hours after start of IMP administration	+30 minutes ^a
	2 to 4 hours after start of IMP administration	+1 hour ^a
	4 to 6 hours after start of IMP administration	+1 hour ^a

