3.7.1.7 Treatment Period (Completion Assessment on Day 6 or Withdrawal Assessment)

The investigator or subinvestigator will conduct the completion assessment at a feasible time on Day 6 as described below. If IMP administration is discontinued before Day 5, the same assessment as the completion assessment on Day 6 will be conducted as the withdrawal assessment on the day after the final IMP administration, whenever possible.

1) At the end of urine collection

- Urine sodium concentration (central measurement)
- Urine osmolality (central measurement)
- Urine potassium concentration (central measurement)

2) At a feasible time

- Serum sodium concentration (local measurement, central measurement)
- Serum potassium concentration (local measurement, central measurement)
- Serum osmolality (central measurement)
- Biomarkers (central measurement)
- Body weight

- Dyspnea (respiratory rate, paroxysmal nocturnal dyspnea, orthopnea, and subject-assessed dyspnea)
- Congestive symptoms (lower limb edema, hepatomegaly, jugular venous distension, pulmonary rales, and cardiac third sound)
- Chest x-ray (cardiothoracic ratio and pulmonary congestion)
- Clinical laboratory tests (central measurement)
- Physical examination
- Vital signs (blood pressure, pulse rate, and body temperature)
- 12-Lead ECG
- NYHA classification
- Adverse Events
- Concomitant medications and therapies

3.7.1.8 Follow-up After End of the Treatment Period (7 to 10 Days After the Final IMP Administration)

The investigator or subinvestigator will conduct the following examinations and tests within 7 to 10 days after the final IMP administration. If the subject has already been discharged from the trial site, the follow-up may be conducted on an outpatient basis.

- Serum sodium concentration (central measurement)
- Serum potassium concentration (central measurement)
- Body weight
- Congestive symptoms (lower limb edema, hepatomegaly, jugular venous distension, pulmonary rales, and cardiac third sound)
- Clinical laboratory tests (central measurement)
- Physical examination
- Vital signs (blood pressure, pulse rate, and body temperature)
- Adverse Events
- Urine pregnancy test (WOCBP only)
- Concomitant medications and therapies

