Body weight	Before IMP administration on Day 1 (Screening values will be used if the values at screening are measured on Day 1 but not measured prior to the IMP administration on that day.)	Day after final IMP administration
Congestive symptoms (lower limb edema, jugular venous distension, hepatomegaly, pulmonary rales, cardiac third sound)	Screening	Day after final IMP administration
Pulmonary congestion, cardiothoracic ratio	Screening	Day after final IMP administration
Respiratory rate, paroxysmal nocturnal dyspnea, orthopnea	Screening	Day after final IMP administration
Subject-assessed dyspnea	Screening	Day after final IMP administration
NYHA classification	Screening	Day after final IMP administration

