### **5.4 Handling of Missing Data**

Missing data at the time of final IMP administration will be imputed using the last available data obtained by the day after the final IMP administration.

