### 8.3.2 Congestive Symptoms

#### 8.3.2.1 Lower Limb Edema and Pulmonary Congestion

The number, and proportion with the two-sided 95% confidence intervals (exact) will be calculated for the improvement rate and the resolution rate at the time of final IMP administration. The improvement rate is defined as the proportion of subjects in whom a symptom is present at baseline and then markedly improves or improves after IMP administration (for the improvement category, see [Table 8.3.2.1-1](#)). The resolution rate is defined as the proportion of subjects in whom a symptom is present at baseline and then resolves after IMP administration.

Shift tables for the severity of the symptoms will be prepared at each on-treatment time point and at the time of final IMP administration compared with baseline.

Table 8.3.2.1-1 Improvement Category of Lower Limb Edema and Pulmonary Congestion		
	Improvement category	Assessment criteria
1	Markedly improved	The symptom resolved or improved by $\geq 2$ categories.
2	Improved	The symptom improved by one category. (Symptom resolution will be categorized as “markedly improved.”)
3	Unchanged	The symptom remained unchanged or was absent throughout the trial period.
4	Deteriorated	The symptom worsened by $\geq 1$ category.

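### The SAP takes the chest X-ray baseline from screening although the protocol schedules a later film before the first dose, so pre-dose change can be counted as change after treatment

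*SAP*

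**What the plan says.** SAP Table 3.4-1 gives the baseline and the final time point for the X-ray variables in one row: "Pulmonary congestion, cardiothoracic ratio Screening Day after final IMP administration".

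The protocol has two pre-drug occasions for this film.

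- **Screening.** Protocol Table 3.7-1 (note i) and Section 3.7.1.1.1 accept a film that predates consent: "Chest x-ray does not have to be repeated if it has been performed within 24 hours before informed consent".
- **Day 1, before dosing.** The predose list in Section 3.7.1.2 includes "Chest x-ray (cardiothoracic ratio and pulmonary congestion"), and the Day 1 cell of Table 3.7-1 carries the symbol for a measurement before the infusion starts. Note e and Section 3.7.1.2 waive this film only when the screening film is taken on Day 1; in that case "the measurements do not have to be repeated at predose on Day 1".

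Body weight and vital signs fall under the same note e. Table 3.4-1 gives both a Day 1 predose baseline, with a fallback: "Screening values will be used if the values at screening are measured on Day 1" and no separate predose value exists.

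SAP 8.3.2.1 defines the improvement rate for pulmonary congestion through subjects in whom "a symptom is present at baseline and then markedly improves or improves after IMP administration". SAP 8.3.2.2 reports the change in cardiothoracic ratio with a t-based 95% confidence interval. Under SAP 5.4, missing data at the final time point are "imputed using the last available data obtained by the day after the final IMP administration".

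**The concern.** The trial has no control group, so change from baseline is the only efficacy contrast. A baseline film that is not the last one before the first dose lets earlier change into a result labelled as change after the investigational product.

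Two features make such change plausible. Subjects are already on injected loop diuretics (inclusion criterion 1). Pulmonary congestion is also one of the three qualifying signs (inclusion criterion 2), and the screening film may be used to establish eligibility, so some drift toward milder grades is to be expected in subjects selected on it.

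Affected are the improvement and resolution rates for pulmonary congestion, its shift table, and the cardiothoracic ratio change with its interval. The direction is plausibly but not certainly favourable: a subject who worsens before dosing and then improves by one grade on treatment is scored as unchanged.

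**Working it through.** The documents state no figure on this point, so there is none to reproduce. The check sets the schedule beside the SAP baseline and then illustrates the size.

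**Schedule against baseline rule**

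| Variable | Scheduled value between screening and first dose | SAP baseline |
|---|---|---|
| Body weight, vital signs | Yes, Day 1 predose, unless screening measured on Day 1 | Day 1 predose, same-day screening value as fallback |
| Pulmonary congestion, cardiothoracic ratio | Yes, same waiver | Screening |
| Edema, jugular distension, hepatomegaly, rales, third sound, dyspnea items | No; the Day 1 assessment falls after the infusion starts | Screening |
| NYHA class | No Day 1 assessment | Screening |

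The X-ray row is the only one with a screening baseline and a later scheduled pre-drug value. The sentence in SAP 3.4 on variables measured several times concerns repeats within a CRF visit and does not override the explicit row. SAP Section 14 discusses only the dose-escalation grouping.

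**Length of the gap.** It is zero if the screening film is taken on Day 1. Otherwise it is at most about 24 h (film before consent) + 24 h (nominal, consent on Day -1) = 48 h.

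**Improvement rate, assumed inputs.** Let s be the share improving a grade before dosing, w the share worsening a grade before dosing, and q the on-treatment improvement rate. Assume independence, no rebound after early improvement, on-treatment improvement of one grade, and two separate films in every subject.

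- Rate with screening baseline = s + (1 - s - w)q
- Rate with predose baseline = q
- Error = s(1 - q) - wq

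Take s = 0.05 to 0.20 and q = 0.40 to 0.60.

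- With w = 0: from 0.05 × 0.4 = 0.02 to 0.20 × 0.6 = 0.12, that is +2 to +12 points.
- With w from 0 to 0.10: the minimum is 0.05 × 0.4 - 0.10 × 0.6 = -0.04 and the maximum stays 0.12, that is -4 to +12 points.
- The error vanishes at w = s(1 - q)/q; for s = 0.05 and q = 0.6 that is 0.033.

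If only a share f of subjects has two films, the error is multiplied by f. At f = 0.25 the range -4 to +12 becomes -1 to +3 points.

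**Resolution rate, assumed inputs.** Let f be as above (0.25 to 1), p the share of those whose congestion clears before dosing (0.05 to 0.20), and r the true resolution rate after dosing (0.30 or 0.50). No worsening is assumed.

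- Rate with screening baseline = fp + (1 - fp)r, so the excess is fp(1 - r).
- Smallest: 0.25 × 0.05 × 0.5 = 0.006. Largest: 1 × 0.20 × 0.7 = 0.14. The range is 0.6 to 14 points.
- Example: f = 0.5, p = 0.10, r = 0.30 gives 33.5% instead of 30%.

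**Cardiothoracic ratio.** The mean change shifts by f times the mean change between the two pre-drug films.

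**Carry-forward.** Protocol 3.7.1.3 to 3.7.1.6 schedule no film between Day 1 predose and the completion or withdrawal assessment. For early stoppers that assessment is "conducted as the withdrawal assessment on the day after the final IMP administration, whenever possible". The efficacy set (SAP 5.3) requires postdose efficacy data but not a postdose film. SAP 5.4 does not restrict the carried value to postdose data, so a missing final film can be filled by the predose film, and the counted change is then wholly pre-drug. Each subject wrongly counted as improved in this way adds 1/40 = 2.5 points if 40 subjects have congestion at baseline, or 1/20 = 5.0 points if 20 do (both denominators assumed).

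**The case against.** The strongest defence is consistency. Every congestion, dyspnea and NYHA row uses screening, and for the X-ray that baseline matches the status on which the subject was enrolled. Moving the film to Day 1 breaks that alignment. The gain is also modest: loop diuretics continue during treatment, so change from a predose film still mixes the product with background therapy and natural course. The effect disappears for subjects screened on Day 1, whose number is unknown, and every percentage above rests on assumed inputs. On carry-forward, SAP 8.3.2.1 speaks of improvement after administration, which a predose film cannot show, and the problem needs both a missing final film and a grade change between the two earlier films.

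Much of this stands as a limit on size. It does not justify the choice. The neighbouring rows use screening because they have no later pre-drug value; the X-ray does, and the SAP gives no reason for passing over it. That the contrast remains confounded is no reason to add a segment that is entirely pre-drug. The wording of 8.3.2.1 points against counting a carried predose film, but SAP 5.4 as written permits it, and the two should not be left to interpretation.

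**Conclusion.** The concern holds. For any subject whose screening film precedes a separate Day 1 predose film, the SAP counts change before the first dose as change after it, and it departs from its own rule for body weight and vital signs without explanation.

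The size is unknown, because the documents give neither the number of subjects with two pre-drug films nor the change between them; the percentage-point ranges are illustrations only. The consequence is limited: no hypothesis test is involved, the SAP sets no primary or secondary outcome variables, and the safety analyses are untouched. It is still worth correcting, because these results are reported with 95% confidence intervals and no control group offsets pre-dose change.

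**What to change.** - In SAP Table 3.4-1, define baseline for pulmonary congestion and cardiothoracic ratio as the last film before the first administration: the Day 1 predose film where taken, otherwise the screening film.
- In SAP 5.4, state that for these two variables only postdose films may be carried to the final time point. Report subjects with no postdose film as missing and give their number. Without this sentence, the new baseline would be carried forward as its own final value and scored as no change.
- Apply both rules to Table 7.3-1 (CT-3.4.1, CT-3.4.2) and to CT-6.1, CT-6.2, CT-6.4, CT-6.7 and CT-6.10.
- Add one line giving the number of subjects whose congestion grade differs between the screening and predose films.

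The cost is one table row, one rule and one line of output, using films the protocol already schedules. Improvement rates may come out slightly lower, a few subjects may be missing at the final time point, and the X-ray baseline will differ in timing from that of the clinical congestive signs. If the sponsor prefers screening, the SAP should state why; the carry-forward restriction is needed either way.
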